11.5 Data Analysis

Evaluation of correlation between diagnostic imaging standard of care and VCI biomarker by an independent core laboratory masked to local radiology determination. Success criteria will include clinical validation of VCI biomarker for LVO detection threshold performance at or exceeding 90% ROC-AUC (targeting SEN & SPE greater than 90%) to standard of care imaging.

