4.18 Data Collection

[figure not shown]
Subjects will have the following data collected:

- *Informed Consent*
- *Subject Demographics*
- *Clinical assessment metrics*
- *Cohort Assignment*
- *Randomization Assignment*
- *Relevant Medical History*
- *Stroke Workflow times (as specified with 'Get with the Guidelines')*
- *NovaGuide System or Lucid M1 System use information*
- *Head inclination (degree)/subject positioning/location of the exam*
- *User (name)*
- *Start/stop time- scan duration*
- *Relevant Concomitant Medications*
- *Device-Related Adverse Events*
- *Device Deficiencies / Technical Observations*

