4.20 Study Workflow

5 MEASURES TO AVOID AND MINIMIZE BIAS

5.1 Imaging Core Laboratory

The objectives of the Core Lab are to provide an unbiased assessment of computed tomography angiography (CTA) to determine presence of large vessel occlusion.

For each subject that received a CTA, the Investigational Site will be instructed to follow a standard procedure developed by the Core Lab for obtaining catheter angiographic images pre-procedure.

Images will be sent directly from the site to the Core Lab. Core Lab definitions and procedures will adhere to specifications documented in the Core Lab Manual of Operations.

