5.2 Imaging Core Lab Blinding

The Core Lab will assess all CT/CTA/MRA imaging blinded to cohort assignment. The Investigational Site will ensure subject identifying information is blinded prior to imaging data submission to the Core Lab. Should it not be possible for a site to blind the information without also deleting/omitting information required for evaluation of the angiography or CT/MRI images, NovaSignal shall have the option to contract with the Core Lab to blind the images. Subject's date of birth will be required in order to identify images provided from the study sites.

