5.3 TCD Waveform Blinding

There are several methods used to blind both the site clinical team and NovaSignal. First, the clinical team will be blinded to the results of the VCI and therefore will not have the ability to influence specific groups. Additionally, the use of the fully automated system (NovaGuide) will further reduce the influence and variability of an individual clinical researcher. Core Lab will make the assessment of the CTA and NovaSignal will be blinded to the comparison of the VCI and CTA results.

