10.5 Case Report Forms

All required data for this study will be collected on standardized Case Report Forms (CRF). The forms may be paper based or electronic. The forms will only include the subject study number assigned once the subject is screened. The investigator is responsible for the accuracy, completeness and legibility of the data reported to NovaSignal in the CRFs and in all required reports. The CRFs are to be dated and signed by an investigator on appropriate pages to verify that he/she has reviewed the recorded data.

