11.2 Phase 2 Statistical Analysis

Primary Endpoint Analysis: Demonstration of VCI biomarker performance at or exceeding 90% ROC-AUC (targeting SEN & SPE greater than 90%) to standard of care imaging across multiple centers.

Here, we will determine the final biomarker performance using the dataset collected and reviewed by the core lab. Similar analyses will be run on the VCI biomarker distributions for the Phase 2 subject group as was done in Phase 1. Additionally, subgroup analyses comparing biomarker results across research sites, and age groups, will be conducted to determine if any age or NovaGuide inter-operator variability effects are present in the data (two-way ANOVA with post-hoc comparisons).

Sample size calculation: In Phase 2, we seek to demonstrate stricter confidence bounds on biomarker diagnostic performance in excess of 90% ROC-AUC. Assuming the biomarker is observed to meet that performance threshold, then a sample of approximately 150 LVO subjects in each patient group is required to attain a one-tailed 95% confidence bound on the observed AUC of 3%. That is, the target AUC and sample size would afford 95% confidence that the underlying general population AUC is greater than 87%. Moreover, across five sites, this results in approximately 30 LVO subjects per site, affording sufficient power for detection of moderate potential inter-site effects in the range of Cohen’s $D \geq 0.75$.

Calculate study and site specific stroke workflow times: Stroke workflow parameters and times are well characterized in literature, including “Get with the Guidelines, Stroke” published by the American Heart Association, Inc. and will be utilized as a historical control comparator for data collected in Phase 2. We will use these published stroke guidelines which have mean times for the stroke workflow parameters to show that we are non-inferior to these when using the NovaGuide device. Additionally, the data will be compared to the corresponding randomized group (Cohort C and D)

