11.4 TCD Data Analysis

All TCD data acquired by the NovaGuide System will be sent to NovaSignal which will provide independent quantitative assessment of all TCD study data. They will be blinded to the study and radiology report data and provide independent review.

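### The stated blinding of the primary VCI–CTA comparison is contradicted by the CRF data flow, left unclear by Section 11.5, and not secured by any lock or access rule

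*Combined protocol and SAP*

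**What the plan says.** **Sponsor (index test).** Section 11.4 sends the TCD data to the sponsor for assessment and says of the assessors: "They will be blinded to the study and radiology report data and provide independent review". Section 5.3 adds: "Core Lab will make the assessment of the CTA and NovaSignal will be blinded to the comparison of the VCI and CTA results". Section 10.5 puts all required data on CRFs and makes the investigator responsible for the "legibility of the data reported to NovaSignal in the CRFs and in all required reports". Section 4.18 lists "Cohort Assignment" among the items collected for each subject. Under Sections 4.6 and 4.16.2, cohort is defined by LVO status on the site's CTA. Section 4.11 has the TCD data reviewed for quality before analysis, without naming the reviewer, the criteria or the timing.

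**Core lab (reference standard).** Section 5.1: "The objectives of the Core Lab are to provide an unbiased assessment of computed tomography angiography (CTA) to determine presence of large vessel occlusion". Section 5.2: "The Core Lab will assess all CT/CTA/MRA imaging blinded to cohort assignment". Section 11.3 repeats for the core lab the blinding sentence used for the sponsor in 11.4. Section 11.5, repeated in the synopsis, then reads: "Evaluation of correlation between diagnostic imaging standard of care and VCI biomarker by an independent core laboratory masked to local radiology determination".

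**Who makes the comparison.** Section 11.2 says: "Here, we will determine the final biomarker performance using the dataset collected and reviewed by the core lab". No statistician, merge step or lock order is named anywhere.

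**The concern.** The study describes itself as having a blinded endpoint, and Phase 2 is meant to support a regulatory submission. Its primary endpoint is the AUC, sensitivity and specificity of VCI against CTA. That comparison is credible only if VCI and the scan-quality decisions are settled without knowledge of LVO status, and the CTA reads without knowledge of VCI.

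VCI is a computed index, so knowing the cohort would hardly alter the calculation itself. It could act on which recordings are used, on which scans pass the Section 4.11 review, and on algorithm or threshold choices. On the reference side, a reader who holds VCI could resolve borderline occlusions toward it. Both routes push the estimated accuracy upward. Blinding the clinical team to VCI, which Section 5.3 provides, closes neither.

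**Working it through.** **Step 1. Index side.**
- The sponsor assesses the TCD data and is stated to be blinded (5.3, 11.4).
- Required data go on CRFs, and CRF data are reported to the sponsor (10.5).
- The collected data include cohort (4.18), which is the site's CTA-based LVO status (4.6, 4.16.2).

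So the organisation said to be blinded receives a close proxy for the reference label. The methods in 5.3 are blinding the clinical team to VCI, automated acquisition, core lab reading of the CTA, and blinding the sponsor to the comparison. None restricts CRF access. De-identification (4.11, 10.4) removes identity, not cohort.

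**Step 2. Reference side.** The only core laboratory that the protocol defines is the CTA reader (5.1, 5.2, 11.3). If 11.5 means that laboratory, it evaluates VCI while masked only to the local radiology reading. That is compatible with the blinding in 11.3 only if its reads are locked before VCI arrives, and no lock is stated. If 11.5 means only that the laboratory supplies the masked read, there is no conflict. The sentence has no verb and does not settle this.

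**Step 3. The plan's own precision figure.** Section 11.2 gives a 3% one-sided bound at AUC 0.90 with 150 per group. The Hanley–McNeil variance, with A the AUC and n per group, is

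[A(1−A) + (n−1)(Q₁−A²) + (n−1)(Q₂−A²)] / n², where Q₁ = A/(2−A) and Q₂ = 2A²/(1+A).

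- Q₁ = 0.9/1.1 = 0.8182; Q₂ = 1.62/1.9 = 0.8526; A² = 0.81.
- SE = √[(0.09 + 149 × 0.0082 + 149 × 0.0426)/22,500] = 0.0185.
- 1.645 × 0.0185 = 0.030, so the lower bound is 0.870.

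The plan's 3% and 87% reproduce. This bound covers sampling error only, not bias from unblinded choices.

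**Step 4. Illustration of size.** Inputs:
- 156 scanned subjects per cohort (synopsis, Phase 2).
- Binormal scores with equal variances, higher values pointing to LVO.
- True AUC 0.87. This is an assumption, set at the lower bound in 11.2. The group separation is √2 × Φ⁻¹(0.87) = 1.593 SD.

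The worst-scoring fifth is the 31 lowest LVO scores and the 31 highest non-LVO scores (156/5 ≈ 31). Percentages moved by a point or two between simulation runs; ranges show this.

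| Change, per cohort | Mean AUC | Chance of AUC ≥ 0.90 |
|---|---|---|
| None | 0.870 | 6–7% |
| 3 or 5 dropped regardless of score | 0.870 | 6% |
| 3 dropped at random from worst fifth | 0.88 | 16–18% |
| 5 dropped at random from worst fifth | 0.89 | 28–29% |
| 8 dropped at random from worst fifth | 0.90 | 53–54% |
| 3 most discordant CTA labels swapped | 0.90 | 50% |
| 5 most discordant scans dropped | 0.91 | 70% |

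Three scans are 3/156 = 1.9% of a cohort, and five are 3.2%.

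**The case against.** The strongest reply is that blinding is stated four times (5.2, 5.3, 11.3, 11.4) and that the documents describe no breach. CRF data normally go to a sponsor, and the assessors in 11.4 may be a separate team. No sentence names who computes VCI, and Section 11.1 is in the passive. The CRF carries the site's reading, whereas the reference is the core lab's. Much of this stands. A reader might infer that the blinding fails on both sides; the text does not show that.

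A reader might also infer from 11.5 that whoever sets the LVO label holds VCI while doing so. No section says that VCI values are sent to the core lab. Masking to local radiology is a natural description of a CTA reader, and 11.2 fits the view that the laboratory only supplies the reference.

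Nor do 5.3, 11.2 and 11.5 give the comparison three different owners. Section 5.3 says only who is blinded to it. At most 11.2 and 11.5 differ, and 11.5 is ambiguous.

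Finally, the largest simulated effects require someone to pick exactly the most discordant cases in both cohorts. Exclusions unrelated to score leave the AUC at 0.870.

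What the reply does not answer is the index side. The plan claims that the sponsor is blinded and also routes cohort to it. A separate team or a restricted view would reconcile the two, but neither is described.

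**Conclusion.** The point holds as a contradiction and a missing safeguard, not as a demonstrated loss of blinding. The index side is the main part and follows from the text of 4.18, 5.3, 10.5 and 11.4. That the sponsor computes VCI is inferred from 11.4, though strongly supported. The reference side is an ambiguity of wording in 11.5 and the synopsis.

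On size, the moderate illustration is the fair one to carry forward: an AUC of 0.88 to 0.89 against a true 0.87, with a chance of reaching the 90% mark of about 16–18% to 29% instead of 6–7%. The 0.91 and 70% are a worst case. All of these rest on the assumed AUC, the binormal model and the assumed selection; they show sensitivity and predict nothing. They do show that discretion over 2% to 3% of scans matters against this success mark.

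This should be fixed before pivotal data are analysed. It does not invalidate the design.

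**What to change.** 1. Reword Section 11.5 and the synopsis so that the core lab supplies only the masked CTA reads, date-stamped and locked before it can receive any VCI value.
2. State who computes VCI and who makes the Section 4.11 quality call. Hide cohort, occlusion location and NIHSS in the CRF/EDC from those staff until all VCI values and quality calls for that phase are locked. The lock must cover the whole phase: release subject by subject would let the sponsor compare VCI with cohort during enrolment, contrary to 5.3.
3. Name a statistician who neither reads CTAs nor processes TCD data to merge the two locked files, and align Sections 5.3, 11.2 and 11.4 with this.

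The cost is protocol wording, EDC access rights and a named role. No extra subjects or image readers are needed. The downside is that TCD staff cannot compare VCI with cohort while a phase is running.

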12 ETHICAL CONSIDERATIONS

12.1 Investigational Review Board (IRB) Approval

This study will be conducted using an FDA cleared product called the Lucid M1 System, 510k K160442 and CE Mark 32518. The study will also utilize an investigational device, called the NovaGuide System, comprised of a NovaGuide System and a research use only software program (that does not alter the FDA cleared/CE Mark approved Lucid M1 System). The study scans are non-invasive. A local Investigational Review Board (IRB) or ethics committee review and approval is required prior to commencement of the study.

This protocol and the informed consent must be reviewed and approved by the appropriate IRB where the study is to be conducted before enrolment of subjects. NovaSignal and the IRB must approve in writing any changes to the protocol that affect the rights, safety, and/or welfare of the subjects, or may adversely affect the validity of the study.

It is the responsibility of the investigator to submit the final version of the protocol with the Informed Consent Form (ICF), if required, to an appropriately constituted IRB prior to commencement of the study. The Investigator will submit the appropriate documentation if any extension, renewal or amendment of the IRB approval must be obtained. In particular, study plan amendments, ICF changes or other written information provided to the subject must be approved by the IRB in writing, when required.

12.2 Role of NovaSignal

As the study Sponsor of this clinical study, NovaSignal has the overall responsibility for the conduct of the study, including assurance that the study meets the regulatory requirements of the Food and Drug Administration. NovaSignal will ensure adherence to the regulations as outlined in the Sponsor general duties, selection of investigators, monitoring, maintaining records, and submitting reports.

12.3 Investigator Responsibilities

The Principal Investigator (PI) shall be responsible for the day-to-day conduct of the study as well as for the safety and well-being of the human subjects involved in the study. The PI also assumes overall responsibility and accountability for the study team and for data obtained from each subject participating in the study.

The PI shall be responsible for:

1. Obtaining a written IRB approval for the study and subject ICF prior to including any subject in this study, as required by local rules and laws.
2. Ensuring that the study is conducted in compliance with IRB requirements including conditions which may be imposed by a reviewing IRB.
3. Ensuring compliance with the study plan, applicable laws, and applicable regulations.
4. Obtaining informed consent and privacy authorization for all study subjects prior to subject participation (the informed consent and privacy authorization processes may be combined, as per usual procedure of the IRB).
5. Collecting all required study data on the Case Report Forms provided.
6. Reviewing and signing CRF pages indicating documents are accurate and complete.

The PI will agree to provide access to the records of all subjects entered into this study, as well as all other study documentation. In addition, all records may be subject to inspection by officials of US FDA and other regulatory authorities according to local rules and laws.

The PI should make accurate and adequate progress reports to the IRB at appropriate intervals, according to the IRB requirements, when applicable. The PI will inform the IRB of study completion or termination within the time period specified by the IRB, when applicable.

The PI is responsible for informing the IRB of any safety issues related to the study as required.

The PI/site must maintain adequate records on all aspects of the study.

The PI/site must maintain the study records for at least two years after cessation of the study.

12.3.1 Records Custody

An investigator may withdraw from the study. If the PI withdraws from the study, the responsibility of conducting follow-up and maintaining records must be transferred to another responsible party within institution (i.e. Sub-I). Notice of transfer must be provided in writing by the PI to NovaSignal and the IRB when applicable, not later than 10 working days after transfer occurs.

12.4 Sub-Investigator (Sub-I) – Responsibilities

Sub-Investigators will be responsible for study activities in coordination with the PI and in accordance to the study plan. A Sub-Investigator may assume the responsibility of the PI should the PI resign from the study.
